13.8 Evaluation of Response

Changes in AFP-L3% will be evaluated for all randomized participants.

13.9 Interim Analysis

There will be no planned interim analyses.

13.10 Ancillary Studies

Not applicable.

14. ETHICAL AND REGULATORY CONSIDERATIONS

14.1 Form FDA 1572

Prior to initiating this study, the Protocol Lead Investigator at the Lead or Participating Organization(s) will provide a signed Form FDA 1572 stating that the study will be conducted in compliance with

regulations for clinical investigations and listing the investigators, at each site that will participate in the protocol. All personnel directly involved in the performance of procedures required by the protocol and the collection of data should be listed on Form FDA 1572.

14.2 Other Required Documents

14.2.1 Current (within two years) CV or biosketch for all study personnel listed on the Form FDA 1572 and Delegation of Tasks form for the Lead Organization and all Participating Organizations.

14.2.2 Current medical licenses (where applicable) for all study personnel listed on Form FDA 1572 and Delegation of Tasks form for the Lead Organization and all Participating Organizations.

14.2.3 Lab certification (*e.g.*, CLIA, CAP) and lab normal ranges for all labs listed on Form FDA 1572 for the Lead Organization and all Participating Organizations.

14.2.4 Documentation of training in Good Clinical Practice for all study personnel listed on the FDA Form 1572 and Delegation of Tasks form for the Lead Organization and all Participating Organizations.

14.2.5 Documentation of Federalwide Assurance (FWA) number for the Lead Organization and all Participating Organizations.

14.2.6 Signed Investigator's Brochure/Package Insert acknowledgement form

14.2.7 Delegation of Tasks form for the Lead Organization and all Participating Organizations signed by the Principal Investigator for each site and initialed by all study personnel listed on the form

14.2.8 Signed and dated NCI, DCP Financial Disclosure Form for all study personnel listed on Form FDA 1572 for the Lead Organization and all Participating Organizations

14.3 Institutional Review Board Approval

Prior to initiating the study and receiving agent, the Investigators at the Lead Organization and the Participating Organization(s) must obtain written approval to conduct the study from the NCI Central IRB (CIRB). Should changes to the study become necessary, protocol amendments will be submitted to the DCP PIO according to DCP Amendment Guidelines. The DCP-approved amended protocol must be approved by the CIRB prior to implementation.

14.4 Informed Consent

All potential study participants will be given a copy of the CIRB-approved Informed Consent to review. The investigator will explain all aspects of the study in lay language and answer all questions regarding the study. If the participant decides to participate in the study, he/she will be asked to sign and date the Informed Consent document. The study agent(s) will not be released to a participant who has not signed the Informed Consent document. Subjects who refuse to participate or who withdraw from the study will be treated without prejudice.

Participants must be provided the option to allow the use of blood samples, other body fluids, and tissues obtained during testing, operative procedures, or other standard medical practices for further research purposes. If applicable, statement of this option may be included within the informed consent document or may be provided as an addendum to the consent. A Model Consent Form for Use of Tissue for Research is available through a link in the DCP website.

Prior to study initiation, the informed consent document must be reviewed and approved by NCI, DCP, the Consortium Lead Organization, CIRB, and the IRB at each Organization at which the protocol will be implemented. Any subsequent changes to the informed consent must be approved by NCI, DCP, the Consortium Lead Organization's IRB, CIRB, and then submitted to each organization's IRB for approval prior to initiation.

14.5 Submission of Regulatory Documents

All regulatory documents are collected by the Consortia Lead Organization and reviewed for completeness and accuracy. Once the Consortia Lead Organization has received complete and accurate documents from a participating organization, the Consortium Lead Organization will forward the regulatory documents to DCP's Regulatory Contractor:

Paper Document/CD-ROM Submissions: Regulatory Affairs Department CCS Associates, Inc. [name] [contact] [contact]

E-mail Submissions: [contact]

Regulatory documents that do not require an original signature may be sent electronically to the Consortium Lead Organization for review, which will then be electronically forwarded to DCP's Regulatory Contractor.

14.6 Other

This trial will be conducted in compliance with the protocol, Good Clinical Practice (GCP), and the applicable regulatory requirements.

APPENDIX A PERFORMANCE STATUS CRITERIA

ECOG Performance Status Scale

Grade	Descriptions
0	Normal activity. Fully active, able to carry on all pre-disease performance without restriction.
1	Symptoms, but ambulatory. Restricted in physically strenuous activity, but ambulatory and able to carry out work of a light or sedentary nature (e.g. , light housework, office work).
2	In bed <50% of the time. Ambulatory and capable of all self-care, but unable to carry out any work activities. Up and about more than 50% of waking hours.
3	In bed >50% of the time. Capable of only limited self-care, confined to bed or chair more than 50% of waking hours.
4	100% bedridden. Completely disabled. Cannot carry on any self-care. Totally confined to bed or chair.
5	Dead.

Karnofsky Performance Scale

Percent	Description	
100	Normal, no complaints, no evidence of disease.	
90	Able to carry on normal activity; minor signs or symptoms of disease.	
80	Normal activity with effort; some signs or symptoms of disease.	
70	Cares for self, unable to carry on normal activity or to do active work.	
60	Requires occasional assistance, but is able to care for most of his/her needs.	
50	Requires considerable assistance and frequent medical care.	
40	Disabled, requires special care and assistance.	
30	Severely disabled, hospitalization indicated. Death not imminent.	
20	Very sick, hospitalization indicated. Death not imminent.	
10	Moribund, fatal processes progressing rapidly.	
0	Dead.	

APPENDIX B LIST OF ABBREVIATIONS

AT:	Adverse Event	
AE AFP		
	Alpha Fetoprotein	
AFP-L3	Alpha Fetoprotein glycoform (third electrophoretic form of lentil lectin-reactive AFP)	
ALP	Alkaline phosphatase	
ALT	Alanine aminotransferase	
AST	Aspartate aminotransferase	
BMI	Body mass index	
CBDF	Complete Blood Count and Automated Differential	
CIRB	NCI Central IRB	
CMPL	Comprehensive Metabolic Panel	
СРК	Creatine Phosphokinase / Creatine Kinase	
CSMC	Cedars-Sinai Medical Center	
CT	Computed Tomography	
CTCAE	Common Terminology Criteria for Adverse Events	
DCA	Deoxycholic acid	
DSMB	Data and Safety Monitoring Board	
ECOG	Eastern Cooperative Oncology Group	
GCA	Glycocholic acid	
GCDCA	Glycochenodeoxycholic acid	
GDCA	Glycodeoxycholic acid Georgetown University/MedStar Georgetown University Hospital	
GU		
HBV	Hepatitis B virus	
HCC	Hepatocellular carcinoma	
HCV	Hepatitis C virus	
HIPAA	Health Insurance Portability and Accountability Act	
HMG-CoA	3-Hydroxy-3-Methylglutaryl-Coenzyme A	
ICF	Informed Consent Form	
IL-6	Interleukin 6	
IRB	Institutional Review Board	
kPa	Kilopascal	
LCA	Lithocholic acid	
MELD	Model for End-Stage Liver Disease	
MRI	Magnetic Resonance Imaging	
NASH	Nonalcoholic steatohepatitis	
NF-kB	Nuclear factor-kappaB	
NWU	Northwestern University	
PT	Prothrombin Time	
RCT	Randomized controlled trial	
ROS	Reactive Oxygen Species	
TCDCA	Taurochenodeoxycholic acid	
UPR	The University of Puerto Rico	
OFIC		

APPENDIX C STUDY DIARY

Statin Therapy to Reduce Disease Progression from Liver Cirrhosis to Cancer

Please bring your completed diary and your study drug supply, including empty bottles, to every study visit. This will help us keep track of your study drug and how well you are tolerating it.

Protocol Number: NWU2015-06-03	Site:	
Participant Study ID:	Participant Name:	
Date Study Drug Dispensed:	Participant Signature:	

Reminder: Do not consume any grapefruit products, including grapefruit, grapefruit juice, grapefruit seed extract, or dietary supplements containing grapefruit, while you are participating in the study.

Instructions

Complete one line in the table for each day you take the study drug. Please contact the study coordinator at <<Study number>> if you have any questions.

- Take your study drug once per day at bedtime or with an evening meal. Take the capsule at the same time every day. Please swallow the capsule whole and do not chew, crush, or open it.
- Record the date and time of day you took the study drug.
- If you notice any side effects such as headache, abdominal pain, constipation, nausea or vomiting, respiratory infection, or mild skin rash, or if you have any other symptoms or comments, please record them in the Side Effects/Comments column and report them to the study staff when they call you.
- If you miss a dose of the study drug, take it as soon as you remember. Do not take the drug if it has been more than 12 hours since you missed your last dose. Wait and take the next dose at your regular time. Do not take 2 doses of the study drug at the same time. Please write the reason for missing a dose in the Side Effects/Comments column.

Day	Date	Time Study Drug Taken	Side Effects/Comments (Please include reason for missed dose)
1		: 🗌 a.m. / 🗌 p.m.	
2		: 🗌 a.m. / 🗌 p.m.	
3		: 🗌 a.m. / 🗌 p.m.	
4		: 🗌 a.m. / 🗌 p.m.	
5		: 🗌 a.m. / 🗌 p.m.	
6		: 🗌 a.m. / 🗌 p.m.	
7		: 🗌 a.m. / 🗌 p.m.	
8		: 🗌 a.m. / 🗌 p.m.	
9		: 🗌 a.m. / 🗌 p.m.	
10		: 🗌 a.m. / 🗌 p.m.	
11		: 🗌 a.m. / 🗌 p.m.	
12		: 🗌 a.m. / 🗌 p.m.	
13		: 🗌 a.m. / 🗌 p.m.	
14		: 🗌 a.m. / 🗌 p.m.	
15		: 🗌 a.m. / 🗌 p.m.	
16		: 🗌 a.m. / 🗌 p.m.	

• For telehealth visits we will ask you to remotely review your pill diary and photograph unused pills

Day	Date	Time Study Drug Taken	Side Effects/Comments (Please include reason for missed dose)
17		: 🗌 a.m. / 🗌 p.m.	
18		: a.m. / p.m.	
19		: 🗌 a.m. / 🗌 p.m.	
20		: a.m. / p.m.	
21		: 🗌 a.m. / 🗌 p.m.	
22		: a.m. / p.m.	
23		: a.m. / p.m.	
24		: 🗌 a.m. / 🗌 p.m.	
25		: a.m. / p.m.	
26		: a.m. / p.m.	
27		: a.m. / p.m.	
28		: 🗌 a.m. / 🗌 p.m.	
29		: a.m. / p.m.	
30		: a.m. / p.m.	
31		: 🗌 a.m. / 🗌 p.m.	
32		: a.m. / p.m.	
33		: 🗌 a.m. / 🗌 p.m.	
34		: a.m. / p.m.	
35		: a.m. / p.m.	
36		: 🗌 a.m. / 🗌 p.m.	
37		: a.m. / p.m.	
38		: 🗌 a.m. / 🗌 p.m.	
39		: a.m. / p.m.	
40		: 🗌 a.m. / 🗌 p.m.	
41		: 🗌 a.m. / 🗌 p.m.	
42		: a.m. / p.m.	
43		: 🗌 a.m. / 🗌 p.m.	
44		: a.m. / p.m.	
45		: a.m. / p.m.	
46		: 🗌 a.m. / 🗌 p.m.	
47		: 🗌 a.m. / 🗌 p.m.	
48		: 🗌 a.m. / 🗌 p.m.	
49		: a.m. / p.m.	
50		: 🗌 a.m. / 🗌 p.m.	
51		: a.m. / p.m.	

Day	Date	Time Study Drug Taken	Side Effects/Comments (Please include reason for missed dose)
52		: 🗌 a.m. / 🗌 p.m.	
53		: a.m. / p.m.	
54		: 🗌 a.m. / 🗌 p.m.	
55		: a.m. / p.m.	
56		: 🗌 a.m. / 🗌 p.m.	
57		: a.m. / p.m.	
58		a.m. / p.m.	
59		: a.m. / p.m.	
60		: a.m. / p.m.	
61		: a.m. / p.m.	
62		a.m. / p.m.	
63		: a.m. / p.m.	
64		: a.m. / p.m.	
65		: a.m. / p.m.	
66		: a.m. / p.m.	
67		: a.m. / p.m.	
68		: 🗌 a.m. / 🗌 p.m.	
69		a.m. / p.m.	
70		: a.m. / p.m.	
71		: 🗌 a.m. / 🗌 p.m.	
72		: a.m. / p.m.	
73		: 🗌 a.m. / 🗌 p.m.	
74		: 🗌 a.m. / 🗌 p.m.	
75		: 🗌 a.m. / 🗌 p.m.	
76		: 🗌 a.m. / 🗌 p.m.	
77		: 🗌 a.m. / 🗌 p.m.	
78		: 🗌 a.m. / 🗌 p.m.	
79		: 🗌 a.m. / 🗌 p.m.	
80		: 🗌 a.m. / 🗌 p.m.	
81		: 🗌 a.m. / 🗌 p.m.	
82		: 🗌 a.m. / 🗌 p.m.	
83		: 🗌 a.m. / 🗌 p.m.	
84		: 🗌 a.m. / 🗌 p.m.	
85		: 🗌 a.m. / 🗌 p.m.	

Day	Date	Time Study Drug Taken	Side Effects/Comments (Please include reason for missed dose)
86		: 🗌 a.m. / 🗌 p.m.	
87		: a.m. / p.m.	
88		: 🗌 a.m. / 🗌 p.m.	
89		: a.m. / p.m.	
90		: 🗌 a.m. / 🗌 p.m.	
91		: a.m. / p.m.	
92		: a.m. / p.m.	
93		: 🗌 a.m. / 🗌 p.m.	
94		: a.m. / p.m.	
95		: a.m. / p.m.	
96		: a.m. / p.m.	
97		: 🗌 a.m. / 🗌 p.m.	
98		: 🗌 a.m. / 🗌 p.m.	
99		: a.m. / p.m.	
100		: 🗌 a.m. / 🗌 p.m.	
101		: 🗌 a.m. / 🗌 p.m.	
102		: 🗌 a.m. / 🗌 p.m.	
103		: a.m. / p.m.	
104		: a.m. / p.m.	
105		: 🗌 a.m. / 🗌 p.m.	
106		: 🗌 a.m. / 🗌 p.m.	
107		: 🗌 a.m. / 🗌 p.m.	
108		: 🗌 a.m. / 🗌 p.m.	
109		: 🗌 a.m. / 🗌 p.m.	
110		: 🗌 a.m. / 🗌 p.m.	
111		: 🗌 a.m. / 🗌 p.m.	
112		: 🗌 a.m. / 🗌 p.m.	
113		: 🗌 a.m. / 🗌 p.m.	
114		: 🗌 a.m. / 🗌 p.m.	
115		: 🗌 a.m. / 🗌 p.m.	
116		: 🗌 a.m. / 🗌 p.m.	
117		: 🗌 a.m. / 🗌 p.m.	
118		: 🗌 a.m. / 🗌 p.m.	
119		: 🗌 a.m. / 🗌 p.m.	
120		: 🗌 a.m. / 🗌 p.m.	

FOR STUDY TEAM USE	ONLY Staff Initials:	
Date study drug dispensed:	Date study drug returned:	
Number of pills/capsules dispensed: Number of pills/capsules returned:		
Number of pills/capsules that should have been taken:		
Discrepancy/notes:		

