5.4 Contraindications

Patients are advised not to consume any form of grapefruit (e.g., juice, fruit, grapefruit seed extract, dietary supplements containing grapefruit) while on simvastatin as grapefruit may increase the blood levels of simvastatin [114]. Participants enrolled in the study will be instructed to avoid all forms of grapefruit.

The combined use of simvastatin with systemic formulations of gemfibrozil, cyclosporine, danazol, lomitapide, verapamil, diltiazem, dronedarone, amiodarone, amlodipine, ranolazine, or strong CYP3A4 inhibitors (e.g., itraconazole, ketoconazole, posaconazole, voriconazole, HIV protease inhibitors, boceprevir, telaprevir, erythromycin, clarithromycin, telithromycin, nefazodone, and cobicistat-containing products) is contraindicated due to an increased risk for myopathy. Patients will be screened for contraindications to simvastatin prior to enrollment in the study. Patients with known active infection with HIV will be excluded from the study. Patients will be advised not to use contraindicated medications during the study and will be reviewed at study visits and during follow-up telephone calls. Participants will be closely monitored for symptoms and side effects to the study drug and will be instructed to call the study doctor immediately if they have a serious adverse reaction.

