5.6 Dose Modification

No dose modifications are planned. The study agent will be stopped in the event of an AE \geq grade 3 considered possibly, probably, or definitely related to the study agent. The study agent will be restarted after resolution. One of the common side effects of statin medication is myalgia (muscle pain with normal Creatine Phosphokinase (CPK) level), and rarely this is associated with statin myopathy (muscle weakness or other muscle injury with or without elevation in CPK level). In randomized controlled trials of standard dose statin therapy, the risk is very low (<1%). We will measure levels of CPK in the blood drawn at the first study visit to establish a patient-specific reference for this indicator of muscle toxicity. During the trial, if the participant reports unexplained muscle pain or weakness, CPK will be tested again to check for elevation.

The study agent will be permanently discontinued in subjects experiencing grade 3 or greater myopathy (unexplained muscle symptoms *and* CPK > 5 times ULN) or hepatotoxicity (ALT or AST > 5 times

ULN) that is considered possibly, probably, or definitely related to the study agent. The study agent will be permanently discontinued in subjects experiencing the following grade 2 hepatotoxicities considered possibly, probably, or definitely related to the study agent: (1) hemorrhage requiring medical attention, and (2) symptomatic fistulas. All other grade 2 hepatotoxicities can be restarted after resolution.

Because dose modification could lead to lack of dose homogeneity that may impair the research objectives, we will stop the intervention in patients who initiate drugs that require dose modifications of simvastatin below 40 mg: lomitapide, verapamil, diltiazem, dronedarone, amiodarone, amlodipine, or ranolazine.

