7.3.3 Telephone Calls and Email/Text Messages

Study participants will be followed during the intervention via telephone calls every four weeks (\pm 7 days) by the clinical research staff to assess compliance and adverse events. Participants who report having taken < 85% of the study drug doses between phone calls, or whose pill count at a study visit reveals < 85% compliance, will be called every two weeks (\pm 3 days) to monitor compliance. In addition, participants will receive a phone call the day before each scheduled study visit to remind them to bring any leftover study drugs and the study diary with them to the visit if it occurs in person. For remote visits patients will be called during the week before their final visit (Visit 4) to remind them to take the study drug every day until the visit appointment.

Participants who opt to receive reminders for study medication intake via email or text messages will be contacted by the study staff during the first week of study and further as needed. The study staff will send emails or text messages on cellular phone; participants will be encouraged to respond to these messages indicating if the study drug has been taken. These responses will be used to assess compliance and will be reviewed during phone contacts. For participants who miss more than one dose of the study drug in a week, the email/text reminders will continue further into dosing period. Since agent compliance is very important during the final week of the intervention, text/email messages will be sent to all study participants who opt to receive these reminders.

The following information with be collected during the telephone calls:

- Compliance review: participants will be asked if they missed any doses of the study medication, and the dates of all missed doses will be recorded.
- Concomitant medications review
- Adverse events: participants will be asked if they have experienced any of the following symptoms to assess adverse events:
 - Upper respiratory infection
 - Headache
 - Abdominal pain
 - Constipation
 - o Nausea
 - o Vomiting
 - Mild muscle aches
- Additional symptoms experienced by participants will be recorded to assess adverse events

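### The diary's catch-all symptom line makes no exception for the serious reactions that Section 5.4 says participants will be told to phone in at once

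*Combined protocol and SAP*

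**What the plan says.** Three parts of the protocol bear on how a participant reports a reaction.

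- **Appendix C, the study diary.** After a list of mostly routine examples, the instruction widens: "or if you have any other symptoms or comments, please record them in the Side Effects/Comments column". The reporting route reads in full: "please record them in the Side Effects/Comments column and report them to the study staff when they call you". The only outgoing contact it offers is the coordinator's number, to be used "if you have any questions".
- **Section 5.4.** Participants "will be instructed to call the study doctor immediately if they have a serious adverse reaction".
- **Section 7.3.3.** "Study participants will be followed during the intervention via telephone calls every four weeks", with a window of 7 days either side. Participants below 85% compliance are called every two weeks, with a window of 3 days.

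Section 5.6 contains the rules that use the report. "The study agent will be stopped in the event of an AE" of grade 3 or higher that is judged at least possibly related. CPK is scheduled only at Visit 1 and is repeated if a participant reports unexplained muscle pain or weakness.

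**The concern.** For a serious reaction the diary and Section 5.4 differ on when it is reported (at the next staff call, or at once), to whom (study staff, or the study doctor) and who places the call. The diary is the sheet that participants fill in every day, so it is the instruction most likely to be in front of them when a symptom appears.

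The other participant sheets in the document do not settle the matter. Appendix D asks for immediate contact, but only about medications. The reminder messages in Appendix G and the appointment letters in Appendices H and I say nothing about reactions.

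What is at stake is the speed of the plan's own safety steps. After baseline, no CPK is scheduled, so a repeat waits on the participant's report. The agent-stop rule likewise cannot act on an event that staff have not heard about.

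**Working it through.** The plan states no figure for reporting delay, so there is none to reproduce. The check has two parts: whether the texts can be reconciled as printed, and how long the diary's route could take.

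**Texts.** The diary line covers all side effects and all other symptoms, so a serious reaction falls inside it. Section 5.4 gives serious reactions a different route. Nothing in the diary tells the reader that a second route exists. The gap is a missing exception; the diary does not prohibit calling.

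**Inputs for timing.**
- Staff calls every 4 weeks = 28 days, ± 7 days (Sections 5.7, 7.1 and 7.3.3).
- Calls every 14 ± 3 days for participants below 85% compliance (Sections 5.7 and 7.3.3).
- Visits 2, 3 and 4 at 1 month ± 14 days, 3 months ± 14 days and 6 months ± 30 days. Assumption: these are taken as days 30, 91 and 182.
- Pre-visit calls 5–7 days before a visit (Section 4.4) and the day before it (Section 7.3.3).

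**Nominal schedule.** Start of dosing, calls and visits fall on days 0, 28, 30, 56, 84, 91, 112, 140, 168 and 182. The gaps are 28, 2, 26, 28, 7, 21, 28, 28 and 14 days, so the longest is **28 days**. The early pre-visit calls would fall on about days 23–25, 84–86 and 175–177. They shorten the first gap but leave 56→84, 112→140 and 140→168 unchanged, so the maximum stays at 28.

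**Window applied to each interval.** 28 + 7 = **35 days**.

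**Calls pinned to a fixed calendar, one early and the next late.** (28(k+1) + 7) − (28k − 7) = 28 + 14 = **42 days**. This can happen with no visit in between. Calls due on days 112 and 140 could fall on days 105 and 147, while Visit 3 closes by 91 + 14 = day 105 and Visit 4 opens at 182 − 30 = day 152. With Visit 4 near its target date, no pre-visit call falls in that gap either.

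**Participants below 85% compliance.** 14 days nominal and 14 + 3 = 17 if the window applies to each interval.

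All of these are upper limits on the wait for someone who uses only the diary's route. A symptom that starts just before a call is reported almost at once.

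**The case against.** The strongest reply is that the two texts work together: the diary is a routine log, and Section 5.4 is the urgent rule. The diary's examples are routine (headache, constipation, nausea, mild rash), and most match what staff ask about on calls. Section 5.4 commits to giving a separate instruction. The consent pages are not in the copy reviewed and may contain it, and staff can give it in person when they go over study requirements and the diary. This stands in part, and it limits what can be claimed. It does not remove the catch-all, which covers serious reactions as printed and does not point to Section 5.4.

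Four stronger readings are tempting and are not supported:

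- *A reader might infer that the diary tells participants to hold symptoms back.* It does not. It names a reporting occasion and does not forbid calling earlier.
- *A reader might infer that participants are never told to call at once.* Section 5.4 says they will be told, and the consent form could not be checked.
- *A reader might take 42 days, and so 42 further daily doses, as the expected delay.* That needs a fixed calendar, one call 7 days early, the next 7 days late, no other contact between them, and a participant with a serious reaction who keeps dosing and contacts nobody. The documents give no basis for expecting that behaviour.
- *A reader might see a breach of the serious-event reporting deadline.* Section 11.2.2 runs its 24 hours from knowledge of the event, so the diary does not conflict with it.

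**Conclusion.** The point holds as a gap between a participant document and the protocol body. The diary's general line takes in serious reactions and gives them a slower route than Section 5.4 does. For a participant who followed only the diary, the wait could nominally reach 28 days, 35 if the window applies to each interval, and 42 only in the fixed-calendar worst case. Visits, pre-visit calls and two-weekly compliance calls shorten it where they intervene.

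These figures rest on the call windows as written, on the conversion of months to days, and on the participant having no other instruction in mind. How often that last condition would hold cannot be judged from the documents. The change is worth making because it is cheap and because the repeat CPK and the agent-stop rule both depend on staff hearing of the event. It has no bearing on the primary analysis or the sample size.

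**What to change.** Reconcile Appendix C with Section 5.4 so that both give participants the same reporting instruction. If Section 5.4 stands as written, repeat its existing sentence in the diary with the study doctor's number, on a line separate from the one for routine symptoms reported at the next call. Make the same change in any Spanish version, and check that the consent form agrees.

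The cost is one line in a participant document and its translation, submitted through the CIRB, for example with the next amendment. It adds no visits, staff or tests. No clinical threshold or rule is proposed.
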